## 5. STUDY DESIGN AND PROCEDURES

## 5.1 Overview

The proposed study design is a prospective, multicenter, randomized, stratified, double blind, placebocontrolled, proof of principal trial to examine the effect of imatinib mesylate on intrasubject VEGF-D, a biomarker associated with LAM disease activity.

The study is designed as a 3 visit study including baseline, 1 month, and 2 month visits. Since most patients with impaired lung function who would be eligible for this study are already on sirolimus, the proposed study would simultaneously address three issues: 1) provide a biomarker rich proof of principle study of imatinib mesylate in LAM, 2) determine if imatinib mesylate is safe when added to sirolimus, and 3) determine if imatinib mesylate controls vascular endothelial growth factor-D (VEGF-D) once sirolimus is removed. Small numbers of individuals are not on sirolimus; however, this proposal would not exclude them to define if there is a treatment response signal to imatinib mesylate alone. A stratified randomization strategy will differentially enroll participants on or off rapamycin at baseline.

At the conclusion of the study, participants will be returned to clinically available LAM therapy chosen with their treating physician. Imatinib will not be available through the investigators after participation in this study.

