## 5.2.1 Timeline

This timeline for this study is 1 years following after study drug is obtained. Grant funding from the Department of Defense has been approved (see attached budget). Imatinib mesylate (Gleevec®) for this study will be provided by Novartis. Placebo drug will be purchased. Enrollment will commence following IRB approval at both MUSC and Columbia University and subsequent approval by the human research protection office (HRPO) of the US Army Military Department. The anticipated enrollment schedule is detailed in the table below.

11	of 27
----	-------

	Year 1		Year 2				Total		
Target Enrollment Pilot	Q	Q	Q	Q	Q	Q	Q	Q	
Study (per quarter)	1	2	3	4	1	2	3	4	
MUSC	-	-	1	2	4	2	1	0	10
Columbia University	-	-	0	2	5	2	1	0	10
Target Enrollment	-	-	1	5	14	18	20	0	20
(Cumulative)									

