## 6.1.3 Imatinib side effects

The most common side effects of imatinib include nausea, diarrhea, headaches, leg cramps, fluid retention, visual disturbances, rash, weight gain, and reduced number of blood cells (any cell line can be affected). Imatinib is an immune suppressant and increases risks of common and uncommon infections.

Severe systolic congestive heart failure is an uncommon but recognized side effect of imatinib and mice treated with large doses of imatinib show toxic damage to myocardiocytes. Hypoxemia has been noted in one individual with LAM.

Since imatinib is mainly metabolised via the liver enzyme CYP3A4, substances such as ketoconazole, itraconazole, clarithromycin, and grapefruit juice can increase the plasma concentration of the drug. Conversely, CYP3A4 inducers like rifampin and St. John's Wort reduce the drug's activity. These medications will be prohibited during the study. A known interaction between imatinib and sirolimus in which sirolimus levels rise will be monitored during the study.

Imatinib also acts as an inhibitor of CYP3A4, 2C9 and 2D6, increasing the plasma concentrations of simvastatin, cyclosporin, pimozide, warfarin, and metoprolol. Imatinib also reduces plasma levels of levothyroxin via an unknown mechanism. INR, Cholesterol, T4, and TSH will be measured during the study for all individuals.

An imatinib dose reduction to 200 mg daily will be permitted should a participant experience persistent side effects.

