## 6.3.1 Procedures for Adverse Events

Event, date of onset, severity, duration, and relationship to sirolimus or imatinb (if it can be determined) will be recorded on the study AE forms. All adverse events will be followed until they are adequately resolved or stabilized, or for 1 month following study completion, whichever comes first.

If an adverse event occurs during a study visit the study coordinator should first insure the participant receives any needed medical attention. If the study coordinator is notified by phone, the coordinator should confirm that the participant has received medical attention. The study coordinator should then notify the site Principal Investigator and complete the Adverse Event Form within seven days of learning of the event. Study coordinators will comply with local regulations and policies when notifying the institutional IRB.

The following general definitions for rating severity should be used for this study:

**Mild:** Awareness of signs or symptoms, but easily tolerated and transient; causing no loss of time from normal activities; symptoms would not require medication or a medical treatment; signs and symptoms are transient.

**Moderate:** Marked symptoms and discomfort severe enough to cause moderate interference with the subject's usual activities. Symptomatic treatment is possible.

**Severe:** Incapacitating with inability to do work or usual activities; signs and symptoms may be of systemic nature or require medical intervention and/or treatment. Hospitalization may be required or prolonged.

The relationship of an AE or SAE to the underlying disease or to the procedure will be attributed using the following definitions:

Not Related: There is no evidence that the event has a relationship to the drug(s).

**Possibly Related**: The event has a timely relationship to the drug(s) used. However, a potential alternative etiology may be responsible for the adverse event.

**Probably Related**: The event has a timely relationship to the drug(s) used and the causative relationship can clearly be established. No potential alternative etiology is apparent.

The number of subjects and observation time in this pilot study is insufficient to develop a composite index or statistical plan for the evaluation of safety endpoints for this study. Therefore, all adverse events, their timing, severity, and attribution will be reported in study reports.

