#### 6.3.3 Procedures for Serious Adverse Events

There are no expected serious adverse events (SAE) in this study. In accordance with 21 CFR Parts 803 and 812, an SAE is defined as any untoward medical occurrence that: results in death, is lifethreatening, requires inpatient hospitalization or prolongation of existing hospitalization, results in persistent or significant disability/incapacity, is a congenital anomaly/birth defect, or requires intervention to prevent permanent impairment or damage. All SAE will be reported to [name] and the Data Safety Monitoring Board Chair in 24 hours after knowledge of the occurrence.

If a serious adverse event (SAE) occurs during a study visit the study coordinator should first insure the participant receives any needed medical attention. If the study coordinator is notified by phone, the coordinator should confirm that the participant has received medical attention. The study coordinator should then notify the site Principal Investigator and complete the adverse event form. All SAE will be reported to [name] and the Data Safety Monitoring Board in 24 hours after knowledge of the occurrence. Study coordinators should comply with local regulations and policies when notifying the institutional IRB. The DSMB will review all SAEs and the Chairperson of the DSMB will notify the HRPO and principal investigator of adverse safety outcome information sufficient to stop the study.

The principal investigator has the obligation to report all serious adverse events to the FDA, IRB, and Novartis Pharmaceuticals Drug Safety and Epidemiology Department (DS&E). All events reported to the FDA by the investigator are to be filed utilizing the Form FDA 3500A (MedWatch Form), if applicable

To ensure patient safety, every SAE, regardless of suspected causality, occurring after the patient has provided informed consent and until at least 30 days after the patient has stopped study treatment must be reported to Novartis within 24 hours of learning of its occurrence. Information about all SAEs is collected and recorded on a Serious Adverse Event Report Form. The investigator must assess and record the relationship of each SAE to each specific study treatment (if there is more than one study treatment), complete the SAE Report Form in English, and send the completed, signed form along with the Novartis provided fax cover sheet to the Novartis Oncology Drug Safety and Epidemiology (DS&E) department by fax ([contact]) within 24 hours.

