## 9.3 Data Safety Monitoring Board

An independent Data Safety Monitoring Board (DSMB) composed of 3 individuals (2 pulmonary specialists and one regulatory/statistical clinical trial specialist) will be established to provide independent benefit/risk oversight during the conduct of the study. The DSMB will: 1) Review the protocol and consent form prior to study initiation, 2) Evaluate Serious Adverse Events on an "as needed" basis and all adverse events on a quarterly basis, 3) Recommend discontinuation of the study in the event of the occurrence of Serious or Unexpected Adverse Events that are determined by the DSMB to pose a significant safety concern. The Chairperson of the DSMB will notify the HRPO and [name] who will in turn notify the FDA or other regulatory bodies of adverse safety outcome information sufficient to stop the study. This information will also be reported as part of required regulatory progress update reports.

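### Severe but non-serious adverse events, and study-drug changes for side effects, reach the DSMB only through a quarterly review, although a full course of treatment lasts 56 days

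*Combined protocol and SAP*

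**What the plan says.** Section 5.1 names three issues for the trial. One is to "determine if imatinib mesylate is safe when added to sirolimus". Each woman takes imatinib or placebo for 56 days. Women on sirolimus continue it up to the 1-month visit and then stop it (5.4).

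Adverse events reach the DSMB at two speeds:

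- **Serious events:** to the DSMB within 24 hours of knowledge (6.3.3).
- **Everything else:** the coordinator tells the site principal investigator and completes the form within seven days (6.3.1). The DSMB then reviews "all adverse events on a quarterly basis" (9.3, repeated in section 6).

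Section 6.3.1 grades an event Severe if it is "Incapacitating with inability to do work or usual activities". Hospitalization is a possible feature of that grade, not a condition of it. Imatinib reduction for persistent side effects is allowed (6.1.3, 6.4), with no separate report to the DSMB.

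The DSMB may "Recommend discontinuation of the study in the event of the occurrence of Serious or Unexpected Adverse Events that are determined by the DSMB" to be a significant safety concern. Section 6.3.1 says the trial is too small and too short for a statistical plan for safety.

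Several safeguards act on the individual woman:

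- both drugs are held for one week for suspected infection (6.4);
- participation ends on a 10% fall in FEV1 or FVC (6.4, 6.4.1);
- 6.4.1 also ends it when symptoms deteriorate;
- a sirolimus level rise above 50% leads to a sirolimus reduction, and the resulting unblinding is reported to the research monitor and the DSMB (5.6).

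The research monitor may halt the research or remove a participant (section 6, 9.4).

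**The concern.** The review interval is longer than the exposure it is meant to oversee. A Severe, non-serious event early in a quarter can wait until the end of that quarter before the DSMB sees it. In the meantime other women can start study drug, pass through the month on imatinib plus sirolimus, and finish.

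This matters more here than in most pilots. Section 2.2 says imatinib has not been used in LAM before, 4.6 describes the trial as primarily a safety study, and 6.1.3 reports a known interaction that raises sirolimus levels. Incapacitating but non-serious toxicity, and drug reductions for side effects, are the early signals that such a trial should expect to act on.

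The period also matters. Sirolimus is stopped at the 1-month visit in both arms, and 2.1 reports rapid deterioration after sirolimus was stopped in an earlier trial. Events before and after that visit can have different causes, and the plan does not say whether the DSMB's listings separate them.

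**Working it through.** **1. Reproduce the accrual plan.** Inputs: the site rows of the table in 5.2.1, where "The anticipated enrollment schedule is detailed in the table below".

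| Accruing quarter | MUSC | Columbia | Both | Cumulative |
|---|---|---|---|---|
| Year 1 Q3 | 1 | 0 | 1 | 1 |
| Year 1 Q4 | 2 | 2 | 4 | 5 |
| Year 2 Q1 | 4 | 5 | 9 | 14 |
| Year 2 Q2 | 2 | 2 | 4 | 18 |
| Year 2 Q3 | 1 | 1 | 2 | 20 |

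The cumulative figures match the table's own row (1, 5, 14, 18, 20).

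**2. Starts between two reviews.** The peak quarter has 9 starts: 9/20 = 45%. This assumes that reviews fall at the ends of accrual quarters. A misaligned three-month window touches two quarters, which together hold at most 4 + 9 = 13 planned starts.

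**3. How many are on imatinib.** Section 6 has 10 sets per arm, with 5 of each sent to Columbia, so 5 of each remain at MUSC. Expected imatinib starts among the 9 are 4 × 5/10 + 5 × 5/10 = 4.5. If allocation within each site is a random draw from its 5 + 5 sets (no smaller blocks, sirolimus strata ignored), the number is 3 to 6 with probability 92%.

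**4. Course against interval.** 365.25/4 = 91.3 days; 91.3/56 = 1.6. A woman who starts in the first 91 − 56 = 35 days or so of a quarter completes all treatment before the next review.

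**5. Chance that a signal arises.** The documents give no rate of Severe non-serious toxicity, so p is an assumption. Among 5 imatinib starts, P(at least one) = 1 − (1 − p)^5:

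- p = 10%: 41%
- p = 20%: 67%
- p = 30%: 83%

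**6. Illustration of the delay.** Assumed inputs: uniform entry within 91.25-day quarters, reviews at quarter ends, 10 women per arm, event onset uniform over Day 0–28 on imatinib only, 20,000 runs. The count is of women randomised after the second event, in those runs that have a second event.

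| Assumed p | Two or more events in 10 | Mean further starts by next quarterly review | Mean further starts within 7 days |
|---|---|---|---|
| 10% | 26% | 2.2 | 0.3 |
| 30% | 85% | 2.8 | 0.4 |
| 50% | 99% | 3.3 | 0.5 |

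These means count both arms. At p = 30% the imatinib share of the 2.8 is about 1.3 to 1.4. The seven-day column counts starts up to the form deadline and allows no time for the DSMB to review or respond.

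**7. Passages that need reconciling.**

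- Section 6.3.3 says "There are no expected serious adverse events (SAE) in this study", while 6.1.3 says "Severe systolic congestive heart failure is an uncommon but recognized side effect of imatinib" and 6.1.4 describes lung toxicity on sirolimus as a serious complication. Section 9.3 relies on the word Unexpected without a reference. Section 6.3.3 does use the Investigator's Brochure or Package Insert as a standard, but only for reports to the drug's manufacturer.
- Section 6.4 has worsening symptoms lead to an evaluation; 6.4.1 has symptomatic deterioration end participation.

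**The case against.** The strongest reply is that the quarterly meeting is not the only protection, and that is right. The safeguards in 5.6, 6.4 and 6.4.1 act without waiting for the DSMB. The lung-function stop also bears on toxicity, since 6.1.4 lists lung toxicity for sirolimus and 6.1.3 mentions hypoxemia. Coordinators telephone at one and two weeks and again after the 1-month visit, the site investigator hears of each event, and the research monitor can stop the trial.

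A reader might therefore be tempted by several stronger readings that the documents do not support:

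- **That nothing written pauses dosing for toxicity.** Section 6.4 holds both drugs for suspected infection, which 6.1.3 names as an imatinib risk.
- **That nobody can act between reviews.** The research monitor can.
- **That nine women would be exposed to imatinib.** About half would be on placebo.
- **That the DSMB sees only pooled data.** The plan is silent on this, and silence does not show it.
- **That the lack of a numerical stopping boundary is itself an error.** Section 6.3.1 openly declines a statistical safety plan, and a judgement-based DSMB is a defensible choice with 20 women.

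It is also fair that the gap is narrower than the Severe label suggests. Any hospitalization makes an event serious, as does significant or persistent disruption of function or quality of life (6.3.2), so many incapacitating events would go by the 24-hour route.

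What remains is the reporting route. Severe events short of that definition exist under the plan's own grading. Neither they nor side-effect reductions are routed to the DSMB faster than quarterly, and none of the material assigned to the research monitor in 9.4 names them. Authority to stop is of little use without prompt notice.

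**Conclusion.** The point holds as a reporting-route weakness. Severe non-serious events and study-drug reductions or stops for side effects have only a quarterly written route to the DSMB, in a trial whose whole course is 56 days and for which safety on top of sirolimus is a stated question.

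The size that rests on the documents is up to 9 of 20 women starting between two reviews, about 4.5 of them expected on imatinib, given aligned quarters and accrual to plan. Section 5.2.1 also gives a one-year timeline beside a two-year table; faster accrual would raise the number. The simulated contrast (about 2.8 against 0.4 further starts) is only an illustration: it depends on an assumed 30% rate, is conditional on two events, and leaves out DSMB response time. Its direction is the same from 10% to 50%.

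This should be changed because it is cheap and bears on participants' safety. It does not undermine the design or show that the trial lacks safety oversight.

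**What to change.** In 9.3 and the matching text of section 6, state that adverse events graded Severe under 6.3.1, and reductions or discontinuations of study drug for side effects, go to the DSMB chair and the research monitor when the adverse event form is completed, within the existing seven-day deadline, and do not wait for the quarterly review. List them by treatment code (A or B) and by period (Day 0–28, Day 28–56). Whether any number of such events should pause the trial is for the DSMB and the investigators; no criterion is proposed here.

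In the same edit:

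- reconcile the statement in 6.3.3 about expected serious events with the recognised harms in 6.1.3 and 6.1.4, and say whether the Investigator's Brochure or Package Insert is the reference for Unexpected in 9.3;
- reconcile 6.4 with 6.4.1 on what follows worsening symptoms.

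The cost is a paragraph of text, an occasional extra e-mail using the existing form and people, and possibly an ad hoc DSMB review.

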## 9.4 Research Monitor

A qualified research monitor, [name], is appointed in accordance with the Department of Defense (DoD) requirements. The research monitor will observe recruitment and enrollment procedures, the informed consent process and may oversee study visits and interactions. The research monitor will review monitoring plans and any unanticipated problem involving risks to subjects or others (UPIRTSO) reports. The research monitor will oversee data collection and analysis. The research monitor may

discuss the research protocol with the investigators, interview human subjects and consult with others outside of the study about the research. The research monitor will have the authority to stop the research in progress, remove individual human subjects from the research protocol, and take whatever steps are necessary to protect the safety and well-being of human subjects until the IRB can assess the monitor's report. The research monitor is responsible for promptly reporting their observations and findings to the IRB and HRPO.

#### **10. STUDY ADMINISTRATION**

The Principal Investigator, [name], oversees study design and implementation. [name] additionally oversees study administration and study personnel, including co-investigator, study coordinator (TBD) and other trained research personnel who will be involved in coordination and execution of this study. Under the auspices of [name] and institutional regulatory bodies trained study staff will coordinate meetings, conference calls, and web-conferences as needed; determine and delegate needs for administrative support (e.g. scheduling, minutes) for committees and subcommittees; ensure fidelity of all data management activities, including form design, regular reports, reimbursing, including contracts, identifying milestones for payment, and generating invoices and payments, maintaining directories and distribution lists, preparing reports, creating recruitment materials and assisting with recruitment, creating and updating the Manual of Operations, training and certification of study personnel, organizing in-person meetings, and coordinating and overseeing the publication process. Consultant funds (see attached budget) will be used for the formation of a Data Safety Monitoring Board, a research monitor and statistical analysis.

